In February 2016, a large university-affiliated pediatric clinic in a low-income urban community introduced Michigan's first pediatric fruit and vegetable prescription program. The program included physician-issued \$15 prescriptions for fresh produce that were distributed after the office visit. Prescriptions were redeemable only for fresh fruits and vegetables at the downtown farmers' market or a local mobile market that traveled throughout the city. Caregivers whose children were exposed to this year-round fruit and vegetable prescription program viewed it as effective in improving child dietary patterns and household food security.²⁸ Moreover, preliminary research, following an expansion of the identical prescription program to a second pediatric clinic, disclosed improvements in food security measures and dietary behaviors of children following one year of exposure to this program.²⁶

In 2018, the US Farm Bill included produce prescription programs, through the Gus Schumacher Nutrition Incentive Program, for the first time.²⁹ The legislation provided federal grant support for new and existing fruit and vegetable prescription programs. Still, these programs continue to focus largely on adults with diet-related chronic health conditions. Few programs are designed specifically to promote healthy eating and prevent disease among vulnerable youth. The current study, conducted across three large pediatric clinics in Flint, Michigan, is designed to provide empirical evidence to evaluate the effectiveness of pediatric fruit and vegetable prescriptions provided to youth and gain insights regarding the duration and intensity of exposure needed to influence changes in food security, dietary patterns, and weight status among children and their caregivers.

Study aims and hypotheses

This study will assess whether exposure to a pediatric fruit and vegetable prescription program (FVPP) that provides one \$15 prescription for fresh produce to every child at each office visit might account for later changes in dietary intake, food security, and weight status.

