- Clinic 3 is the largest pediatric clinic in Genesee County, with Flint as its urban center. Expansion of the FVPP to clinic 3 will substantially increase program reach among vulnerable children and families living in Flint. Last year, clinic 3 had over 12,000 pediatric visits. It has a comparable patient population to clinics 1 and 2, serving only children in need who are residents of Genesee County.

Participants and recruitment

A sample of 250 caregiver-child dyads presenting at clinic 1, 250 caregiver-child dyads at clinic 2, and 350 caregiver-child dyads at clinic 3 will be assessed for eligibility, with 700 total dyads enrolled (anticipated 10-15% not meeting eligibility and 10% refusal based on a previous study). To control for confounders, we will adopt a balancing strategy that consists of recruiting in the study children who have approximately the same age, sex, and race across the three clinical settings. These children will not be balanced according to variables pertaining directly to the exposures (e.g., duration of FVPP exposure).

With target samples of 200, 200, and 300 caregiver-child dyads enrolled in clinic 1 - high exposure, clinic 2 - moderate exposure, and clinic 3 - no previous exposure, respectively, we have well above 90% power to jointly detect modest relative differences in the baseline mean intake of vegetables of 20% from clinic 2 to clinic 3 and 38% from clinic 1 to clinic 3. This calculation assumes an underdispersed Poisson model with a dispersion parameter of 0.82, derived using previously published data on the mean intake of vegetables of 0.72 cup and a standard deviation of 0.77 cup in the settings with no prior FVPP exposure.²⁰ Likewise, with 300 caregiver-child dyads enrolled in clinic 3, we have well above 90% power to detect a modest temporal improvement in the mean intake of vegetables of 25% over 12 months (0.72 cup at baseline versus 0.90 cup at 12-month follow-up). This calculation assumes a correlated Poisson model for underdispersed count data with timepoint dispersion parameter of 0.82, and a modest temporal correlation of 0.2. Increasing values of the temporal correlation greatly improves the statistical power. Finally, estimation of FVPP effects will specify two-tailed tests with alpha set at the 0.05 level.

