An alternative balancing strategy based on propensity scores will be used to mitigate potential differences at baseline among participants in the three study groups. These scores will be used to derive an unbiased estimate of the average treatment effect of FVPP on study endpoints. The generalized propensity score to account for multiple levels of treatment in the spirit of Imbens will be estimated with a multinomial logistic regression.⁶² To estimate the FVPP effects, we will use an elaborated multinomial logistic model that includes the child's level, the caregiver's level covariates, and functions thereof (e.g., interactions).

The choice of analytic methods will be guided by the specific aims, the nature of study endpoints and that of relevant data. Independence models will be used to compare baseline dietary intake, food security, and weight status between pediatric patients with varying levels of exposure to the FVPP. Correlated data models will be used to evaluate (1) changes in diet, food security, and

weight status when never-exposed children are introduced to the FVPP; and (2) compare mean follow-up measures of dietary intake, food security, and weight status in the initial no exposure group to baseline measures in the high exposure group.

Comparison of baseline measures based on FVPP exposure

Multiple linear regression will be used to assess the relationship between mean daily intake of fruits and vegetables and level of exposure to the FVPP. A basic logistic regression model will be used to evaluate the adjusted effect of the child-level exposure to the FVPP on the obesity probability. An ordinal logistic regression model will be used to evaluate the adjusted effects of the child-level exposure to the FVPP on food security (measured as an ordinal outcome). Within this class of models, we will entertain the popular proportional odds model with prior evaluation of the assumption of the proportionality of odds across the ordered levels of food security. These analyses will be adjusted for variables such as food assistance program participation, nutrition education program participation, child race, child age, child gender, caregiver-reported income group, caregiver-reported weight status, caregiver education, and child-reported mean daily intake of fruits and vegetables.

Evaluation of changes when children are introduced to the FVPP

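### The single power figure for the baseline comparison holds for a joint test and for clinic 1 versus clinic 3, but not for the named 20% difference between clinics 2 and 3 or for finding both differences

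*Combined protocol and SAP*

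**What the plan says.** The power statement under Participants and recruitment begins "With target samples of 200, 200, and 300 caregiver-child dyads enrolled in clinic 1 - high exposure, clinic 2 - moderate exposure", with 300 at clinic 3 (no previous exposure). It claims "well above 90% power to jointly detect modest relative differences in the baseline mean intake of vegetables of 20% from clinic 2", as compared with the unexposed clinic. A second difference, 38%, is named between clinics 1 and 3, and each is worded as running from the exposed clinic to the unexposed one. The model is a Poisson model with dispersion 0.82, based on a "mean intake of vegetables of 0.72 cup and a standard deviation of 0.77 cup in the settings with no prior FVPP exposure". Tests are two-tailed at 0.05. The paragraph does not define what joint detection means and gives no clinic means for the two percentages.

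The analysis section on comparison of baseline measures plans multiple linear regression "to assess the relationship between mean daily intake of fruits and vegetables and level of exposure to the FVPP". It specifies neither a joint test of the three levels nor any pairwise contrast. The Background says the study is meant to "gain insights regarding the duration and intensity of exposure needed" to change food security, diet and weight status.

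**The concern.** The sentence names two differences and attaches one power figure to them. A reader may take it that the study is well placed to find each one. The two differ greatly in size, and a joint test can reject because of clinic 1 alone. Such a rejection would not show that the 20% difference at clinic 2 had been detected.

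This matters because clinic 2 versus clinic 3 is the only baseline comparison of 12 to 24 months of exposure with none. If its power is well below the quoted figure, a non-significant result says much less about moderate exposure than the power paragraph would lead a reader to think.

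**Working it through.** **Inputs (all from the power paragraph).** Clinic 3 mean 0.72 cup; SD 0.77; dispersion 0.82 (check: 0.77²/0.72 = 0.823); n = 200, 200, 300; two-sided 0.05.

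**Base of the percentages.** Two readings are possible:
- A, exposed clinic as base: clinic 2 = 0.72/0.80 = 0.90; clinic 1 = 0.72/0.62 = 1.161.
- B, clinic 3 as base: clinic 2 = 0.72 × 1.20 = 0.864; clinic 1 = 0.72 × 1.38 = 0.994.

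**Variance of a clinic mean:** 0.82 × mean / n.
- Clinic 3: 0.82 × 0.72/300 = 0.001968.
- A: clinic 2 0.003690, clinic 1 0.004761.
- B: clinic 2 0.003542, clinic 1 0.004074.

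**Pairwise tests.** z = difference / √(sum of the two variances); power = Φ(z − 1.96).

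| Contrast | Base | Difference | SE | z | Power |
|---|---|---|---|---|---|
| Clinic 1 v 3 | A | 0.441 | 0.0820 | 5.38 | >99% |
| Clinic 1 v 3 | B | 0.274 | 0.0777 | 3.52 | 94% |
| Clinic 2 v 3 | A | 0.180 | 0.0752 | 2.39 | 67% |
| Clinic 2 v 3 | B | 0.144 | 0.0742 | 1.94 | 49% |

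**Reproducing the plan's figure: joint test on 2 degrees of freedom.** The noncentrality is d′S⁻¹d, where d holds the two differences from clinic 3 and S is their covariance matrix (covariance 0.001968, from the shared clinic 3). It is 29.45 under A and 13.01 under B. Against the critical value 5.99, power is **99.9%** (A) and **91%** (B). Clinic 1 v 3 alone supplies z² = 5.38² = 28.9 of the 29.45, or 3.52² = 12.4 of the 13.01, so the joint test gains little from clinic 2.

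**Both contrasts significant.** The two z statistics have correlation 0.001968/(SE₁ × SE₂), which is 0.32 (A) or 0.34 (B). The bivariate normal probability that both exceed 1.96 is **67%** (A) or **48%** (B).

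**Constant SD 0.77,** which is closer to the planned linear regression. SE = 0.77 × √(1/200 + 1/300) = 0.0703. For clinic 2 v 3, z = 2.56 (A) or 2.05 (B), so power is 73% or 54%. For both contrasts it is 73% or 53%.

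**Log scale.** For clinic 2 v 3, z = 2.44 or 1.97, giving 68–69% or about 50%, so the choice of scale hardly matters.

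**Smallest detectable clinic 2 v 3 difference.**
- At 35% over 0.72 (mean 0.972): SE = √(0.82 × (0.972/200 + 0.72/300)) = 0.0772; z = 0.252/0.0772 = 3.27; power 90%.
- At 30% (mean 0.936): z = 2.83; power 81%.

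Expressed with clinic 2 as base, these are 0.252/0.972 = 26% and 0.216/0.936 = 23%.

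**The case against.** The plan claims joint power, and joint power reproduces. A single test of both contrasts is a standard meaning of the phrase, and the plan never claims 90% for clinic 2 v 3 on its own. The wording runs from the exposed clinic to clinic 3, which suits base A. The 0.90 cup implied for clinic 2 under A is also the 12-month value in the next power calculation, where it is called a 25% improvement because 0.72 is the base there. Under A the joint power is 99.9%, which is well above 90%. All of this stands.

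It can also be said that the plan expects a gradient with exposure, and that duration is studied longitudinally in Aims 2 and 3 as well. A linear trend over scores 0, 1, 2 has slope 0.218, SE 0.040, z = 5.42 (A), or slope 0.137, SE 0.038, z = 3.58 (B): power above 99.9% or 95%. That stands too, but neither a trend test nor a joint test is named in the analysis section, and neither isolates the moderate level.

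A reader might go further and infer that the figure is a miscalculation, or that power falls short for both named differences. The documents support neither: the joint figure can be reproduced, and clinic 1 v 3 has 94% or more. Nor does the plan say that a non-significant clinic 2 v 3 result would be read as no effect. That is a risk of leaving the paragraph as it is, not something the plan proposes.

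**Conclusion.** The concern holds in a limited form. The quoted power is right for a 2-df joint test (99.9% or 91%) and for clinic 1 v 3 (over 99% or 94%). It does not carry over to the named clinic 2 v 3 difference (67% or 49%; 73% or 54% with constant SD) or to finding both differences (67% or 48%; 73% or 53%). In each pair the first figure takes the exposed clinic as base, which the text favours. On that base and the plan's dispersion model, a true 20% difference at clinic 2 would be missed about one time in three; on the other base, about one in two.

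The figures assume full enrolment of 200/200/300, no multiplicity adjustment (none is stated), no gain or loss from covariate adjustment, and no confounding of exposure with clinic.

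**What to change.** Revise the power paragraph under Participants and recruitment:

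1. Tie the joint figure to a 2-df test of exposure level, and name that test in the baseline analysis section.
2. State the base by giving the means: 0.90 and 1.16 cup v 0.72 (power 99.9%), or 0.864 and 0.994 v 0.72 (power 91%).
3. State separately that clinic 2 v 3 alone has about 67% (or 49%) power, with a smallest detectable difference of about 35% over 0.72 cup at 90% power and 30% at 80%.
4. Commit to reporting a non-significant clinic 2 v 3 result with its confidence interval and not as absence of effect.

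The cost is some redrafting and a less favourable stated figure. No extra participants are needed, and the regression model is unchanged.

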This study will include a cross-sectional analysis of data from a consecutive sample of caregiver-child dyads with varying levels of exposure to a fruit and vegetable prescription program (FVPP) that provides one \$15 prescription for fresh produce to every child during pediatric office visits. Considering the importance of dietary patterns during childhood on long-term diet and health¹¹⁻¹³ alongside evidence that indicates adolescence is the specific period when food insecurity has the greatest potential to negatively impact the diet,³⁵ data collection and analyses will focus specifically on children and adolescents ages 8-16 years. A total of 700 caregiver-child dyads (one caregiver and one child per household) will be enrolled in the study, with approximately 200 dyads enrolled at clinic 1 (high exposure); 200 dyads enrolled at clinic 2 (moderate exposure), and 300 dyads enrolled at clinic 3 (no previous exposure to the FVPP). A description of the clinics is provided with our explanation of the 'Setting' for this study.

Dyad enrollment will be based on exposure to the FVPP as defined by caregiver-reported and clinic-verified length of time that the participating child has been a patient at one of three partnering clinics. Accordingly, we expect dyads to cluster based on pediatric clinics as follows: clinic 1 (high exposure), clinic 2 (moderate exposure), and clinic 3 (no previous exposure). A sample of approximately 200 pediatric patients newly exposed to the FVPP at clinic 3 will be followed for a period of two years as part of a non-controlled longitudinal intervention trial that will examine changes in dietary patterns, food security, and weight status over time.

Setting

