To compare baseline dietary intake, food security, and weight status between pediatric patients with varying levels of exposure to the FVPP, we will collect study measures at baseline from 700 dyads at each of three partnering clinics. To measure changes in diet, food security, and weight status when never-exposed children are introduced to the FVPP, we will follow approximately 200 dyads from clinic 3, collecting study measures at baseline, 12- and 24-month follow-up. In addition to posters, brochures, and websites that explain the FVPP, caregivers at clinic 3 will be reminded of each follow-up visit through reminder cards and telephone calls.

REDCap provides data security measures designed to prevent unauthorized access, disclosure, alteration, and use of data. Data from the completed evaluation tools will be stored in REDCap project database. Children and caregivers will be assigned identification numbers upon enrollment in the study. All data will be de-identified within the data management system, and de-identified data will be exported for analyses.

Any modifications to the approved protocol will be submitted to Michigan State University IRB for review and approval prior to implementation. Furthermore, although the likelihood of any adverse event in this trial is remote, we have formalized our Data and Safety Monitoring Plan to include a designated Data and Safety Monitor. This Monitor will have the authority to recommend termination of the trial if he makes the determination that unacceptable adverse events have taken place. Should any adverse events occur, these will be immediately reported to Michigan State University IRB for review.

Benefits

Completion of our study aims will provide empirical evidence for the effectiveness of Produce Prescription Programs, which were recently added to the US Farm Bill through the Gus Schumacher Nutrition Incentive Program. Our study will share insights regarding the duration and intensity of exposure necessary to influence changes in food security, dietary patterns, and weight status when fruit and vegetable prescriptions are provided to pediatric patients. Furthermore, our results will be especially important to pediatricians and primary care physicians who recognize the consequences of food insecurity among young patients and are seeking tangible solutions that not only provide food to hungry children but ensure that the food provided is high in nutrients needed to support healthy growth and development.

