After baseline data collection, periodic follow-up assessments will be conducted to study changes in diet, food security, and weight status among children newly exposed to the FVPP at clinic 3. Because of the repeated nature of the data generated for this aim, we will consider methods that accommodate the within-child and/or the within-caregiver association. For continuous outcomes (e.g., dietary intake), repeated measures models such as linear mixed models and repeated ANOVA models, will be entertained in view of their robustness to certain types of missing data. These classes of models will be used to assess changes from baseline at key points in the study.^{63,64} For ordinal endpoints such as food security (with ordered levels), a generalized linear mixed effects model with cumulative logits will be entertained. To examine whether there is a significant improvement in child-reported food security from baseline, contrast representing the difference in log-odds between baseline and follow-up will be evaluated. Alternatively, GEE counterparts of these likelihood-based models (that use the sandwich-based correction in lieu of the model-based variance-covariance matrix of the parameter estimates) will also be considered.⁶⁵

Comparison of mean follow-up measures in the initial no exposure group to baseline measures in the high exposure group

At follow-up, measures of dietary intake, food security, and weight status in a group of children newly exposed to the FVPP will be compared to baseline measures of children with high exposure to the FVPP (>24 months). For example, to compare measures of dietary intake (at 12 months and 24 months) in the newly exposed group to those of the highly exposed group, the class of linear mixed models and repeated ANOVA models will be considered. These models will be similar to those of aim 2, with the additional flexibility of group-specific time-point effects. For ordinal outcomes (e.g., food security) and binary outcomes (e.g., obesity), a generalized linear mixed effects model will be used. Alternative models such as GEE models will also be entertained.

Discussion

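### The 12-month power claim of well above 90% uses 300 dyads when about 200 are followed; the plan's inputs give about 86-89% at 300 and 69-80% at 200

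*Combined protocol and SAP*

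**What the plan says.** The power statement for Aim 2 (change after never-exposed children are introduced to the program) is in Participants and recruitment: "with 300 caregiver-child dyads enrolled in clinic 3, we have well above 90% power to detect a modest temporal improvement". The improvement is 25% in mean vegetable intake, "0.72 cup at baseline versus 0.90 cup at 12-month follow-up". The inputs are given in the same paragraph:

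- Variability: "mean intake of vegetables of 0.72 cup and a standard deviation of 0.77 cup" in settings without prior exposure.
- Model: "This calculation assumes a correlated Poisson model for underdispersed count data with timepoint dispersion parameter of 0.82, and a modest temporal correlation of 0.2".
- Test: "estimation of FVPP effects will specify two-tailed tests with alpha set at the 0.05 level".

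The paragraph adds that a higher correlation would raise the power considerably.

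Two other sections give the number followed. Study Design says: "A sample of approximately 200 pediatric patients newly exposed to the FVPP at clinic 3 will be followed for a period of two years". Data collection procedures says: "we will follow approximately 200 dyads from clinic 3", with measures at baseline, 12 and 24 months.

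For the analysis of change in continuous outcomes such as dietary intake, the statistical analysis plan says that "repeated measures models such as linear mixed models and repeated ANOVA models, will be entertained", with GEE as an alternative. No power is given for 200 dyads, and no attrition rate links 300 to 200.

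**The concern.** A before/after change can be estimated only from children who have a follow-up measurement. The power statement counts everyone enrolled at clinic 3, while the follow-up plan covers about two thirds of them. Separately, the stated inputs are complete enough to recompute the power, and the result falls below the claim even at the larger number.

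This is the only power statement for Aim 2. A reader who accepts it would take a null 12-month result as strong evidence against a 25% rise in vegetable intake. If the real power is nearer 70%, a null result says much less. The Discussion expects the results to inform policy on nutrition prescription programs, so that misreading could matter.

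**Working it through.** **Inputs** (all from Participants and recruitment unless noted): means 0.72 and 0.90 cup, difference 0.18; baseline SD 0.77; dispersion φ = 0.82; correlation ρ = 0.2; two-sided α = 0.05, critical value 1.96; n = 300 in the power statement, about 200 followed (Study Design; Data collection procedures).

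**Step 1: what the dispersion means.** 0.77²/0.72 = 0.5929/0.72 = 0.823. This reproduces the plan's 0.82, so the parameter is variance divided by mean, and the variance rises with the mean.

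**Step 2: formula for complete pairs.** With v₀ and v₁ the variances at baseline and 12 months:

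- Var(diff) = v₀ + v₁ − 2ρ√(v₀v₁)
- SE = √(Var(diff)/n)
- Power = Φ(0.18/SE − 1.96)

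**Step 3: the plan's model, v = 0.82 × mean.** Var(diff) = 0.82(0.72 + 0.90) − 2(0.2)(0.82)√(0.72 × 0.90) = 1.064.

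- n = 300: SE = 0.0596, z = 3.02, power **85.6%**
- n = 200: SE = 0.0730, z = 2.47, power **69.4%**

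A log-link Wald test gives about 85% and 69%.

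**Step 4: a more favourable variance, SD 0.77 at both times.** This is not the plan's model; it is included as a generous bound. Var(diff) = 2(0.5929)(1 − 0.2) = 0.949.

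- n = 300: power **89.3%**
- n = 200: power **74.3%**

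**Step 5: a mixed model using 300 baselines and 200 follow-ups.** With c = ρ√(v₀v₁) and known variances, the generalised least squares variance of the change is

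v₀/300 + v₁/200 − ρ²v₁(1/200 − 1/300) − 2c/300.

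- Dispersion 0.82 (v₀ = 0.5904, v₁ = 0.738, c = 0.132): SE = 0.0688, z = 2.62, power **74.5%**
- Constant SD: SE = 0.0641, z = 2.81, power **80.2%**

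| Data used | Dispersion 0.82 | SD 0.77 at both times |
|---|---|---|
| 300 complete pairs | 86% | 89% |
| 200 complete pairs | 69% | 74% |
| 300 baselines, 200 follow-ups | 74% | 80% |

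**Step 6: simulation.** Correlated underdispersed counts with variance/mean 0.82 (20,000 runs) gave about 86% at 300 pairs and 70% at 200. Gamma margins with correlation 0.2 (20,000 runs) gave, for dispersion 0.82 and constant SD respectively, 85% and 88% (300 pairs), 69% and 75% (200 pairs), and 75% and 81% (300 baselines, 200 follow-ups).

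**Step 7: what would reach 90%.**

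- A one-sided 0.05 test at 300 pairs gives 92-94%, but the plan specifies two-tailed tests.
- Treating 0.82 as a scale to be squared gives 92-94% at 300, but Step 1 shows it is already variance/mean.
- At ρ = 0.2, 90% power needs 308 (constant SD) to about 346 (dispersion 0.82) complete pairs.
- At 300 pairs, 90% needs ρ of 0.22 to 0.31. At 200 pairs it needs 0.48 to 0.54, or 0.42 to 0.51 if all 300 baselines are used.
- At 200 complete pairs with dispersion 0.82, the detectable rise is about 29% for 80% power and 33-34% for 90% (27% and 31% with constant SD).

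**The case against.** The strongest defence concerns the shortfall at 300. It is small (1 to 4 points below 90%) and disappears at a correlation of 0.22 to 0.31. The plan calls 0.2 modest and notes that higher values help. It also does not give the test or variance formula behind its correlated Poisson model, so any recomputation uses an assumed approximation. This is fair, and it makes this half of the point the lesser one. But several approximations and two simulations agree, none of the two-sided calculations from the stated inputs reaches 90%, and the claim was well above 90%.

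For the 300/200 mismatch, a mixed model can use the 100 baseline-only dyads, and 200 may be the number expected to remain after losses from 300. The first is already credited and gives 74-80%; the upper end also needs a constant SD, which departs from the plan's dispersion model. The second is possible, but the plan does not say so, and it would not rescue the figure, because power depends on those measured at 12 months.

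The calculation covers vegetable intake only. It says nothing directly about fruit intake, food security or weight status, for which the plan gives no power.

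**Conclusion.** The point stands. On the plan's own model and follow-up number, power for the 12-month change in vegetable intake is about 69% with 200 complete pairs, and at most about 80% when both favourable assumptions are granted (constant SD, all 300 baselines used). That puts the chance of missing the assumed 25% rise at about 20-31%, at least twice what the plan implies. If all 300 were measured at 12 months, power would be 86-89%, still not above 90%.

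These figures assume ρ = 0.2, a two-sided 0.05 test, a normal approximation, and 200 as the number measured at 12 months. If 200 is instead the number entering follow-up and 10-20% are lost (an assumption; the plan gives no rate), power falls to about 60-70% for complete pairs and 67-77% with all 300 baselines.

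**What to change.** Replace the 12-month power sentence in Participants and recruitment with one tied to the number measured at 12 months and one declared model, for example:

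> With about 200 clinic 3 dyads measured at 12 months, power to detect a rise in mean vegetable intake from 0.72 to 0.90 cup (two-sided 0.05, dispersion 0.82, correlation 0.2) is about 69% for complete pairs, and about 74% if a mixed model also uses all 300 baselines. With complete pairs, 80% power requires a rise of about 29%.

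The constant-SD figures (74% and 80%) and the correlation needed for 90% (0.48-0.54 with complete pairs) can be added as sensitivity results. State whether the 200 are those entering or completing follow-up, with an attrition allowance if entering.

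If the intention is to follow all 300, change Study Design and Data collection procedures to match and state 86-89%.

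The restatement costs one paragraph and a less favourable figure, with no extra enrolment. If 200 is a planned subset, following all 300 would add about 100 dyads to follow-up and would still not reach 90% at a correlation of 0.2.
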